- Abrasive rubber tip will be used to smoothening and rounding the internal angles giving a polished and smoothed preparation.
- Endocrown will be manufactured using CAD/CAM technology
- internal wall of crown will be treated with etchant material, rinsed, dried then silane coupling agent

- Dual-cure resin cement will be applied on the crown fitting surface for endocrown cementation.

Group B: Preformed Bioflex crowns ⁽¹⁰⁾

According to manufacturer instruction the preparation will be as the follow:

- Light -cured glass ionomer filling of adequate thickness will be applied over the ZOE to seal the cavity before preparation
- A digital caliper will be used to measure a mesio-distal dimension of tooth then suitable sized preformed crown will be selected.
- Tooth preparation will be carried out with a tapered diamond bur for occlusal reduction by 1–1.5 mm, including the central groove.
- The proximal preparation will be around 0.5 mm to clear the contact area
- Placement of the crown will be achieved by a snug fit followed by contouring using a Hover's plier.
- Crown cementation will be carried out using glass ionomer cement and removal of excess cement using floss or explorer.

Group C: performed zirconia crowns ^(10, 12, 13)

- Light -cured glass ionomer filling of adequate thickness will be applied over the ZOE to seal the cavity before preparation.
- A digital caliper will be used to measure a mesio-distal dimension of tooth then suitable sized preformed crown will be selected.

- A diamond bur will reduce the occlusal surface by 1.5–2 mm
- Interproximal contacts will be prepared with a tapered fissure bur. About 1–2 mm sub gingival preparation will be performed
- The selected crown will be placed and checked.
- The passive fit of the crown will be assessed and will be luted with glass ionomer cement.
- Consistent firm finger pressure will be applied during cementation.

Observations:

Clinical Performance Assessment ^(10,12)

- Retention, marginal adaption, fracture of the restoration were scored using a modified United States Public Health Service (USPHS) criterion.
- Dental plaque accumulation and gingival condition were assessed using plaque index (PI) and GI.
- Preparation time and cementation assessment using stop watch to record time from preparation start till final restoration cementation.⁽¹⁵⁾

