- Clinical performance and oral status will be assessed at follow-up periods of 3 (T1), 6 (T2), and 12 (T3) months. At the end of the follow-up (T3), parent's satisfaction analysis toward the color, shape, and size of three restorations will be adopted to directly evaluate their satisfaction toward their children's restorations. Parents' responses were rated on a 5-point Likert-type scale.

Microbiological analysis: ⁽⁹⁾

- The swabs will be collected before preparation of crowns, 3 months, 6 months and 12 months after cementation.
- The number of Streptococcus Mutans, lactobacillus will be digitally counted.
- Swabs will be taken from occlusal surface by means of the tips of sterile cotton
- All specimens were transported immediately to microbiological lab.
- Swabs will be taken from occlusal surface by means of the tips of sterile cotton.
- Samples will be preserved in a transporting medium tube containing 9ml thioglycolate broth medium.
- The number of Streptococcus Mutans, lactobacillus will be digitally counted.

Data Management and Analysis

Data will be analyzed using IBM SPSS advanced statistics (Statistical Package for Social Sciences), version 27 (SPSS Inc., Chicago, IL). Numerical data will be described as mean and standard deviation or median and range. Data will be explored for normality using Kolmogorov-Smirnov test and Shapiro-Wilk test. Comparisons between 3 groups for normally distributed numeric variables will be done using the ANOVA while for non-normally distributed numeric variables will be done by Kruskal Wallis test. An equivalence limit will be checked in the difference between groups. Categorical data will be described as numbers and percentages and comparisons will be done by chi square test or fisher exact as appropriate. A p-value less than or equal to 0.05 will be considered statistically significant. All tests will be two tailed.

References

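### Up to 25 three-group comparisons are each judged at 0.05 with no primary outcome, primary time point or multiplicity rule, so the chance of at least one false crown difference is roughly 36–72%, not 5%

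*Combined protocol and SAP*

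**What the plan says.** The Data Management and Analysis section sets the tests and the threshold. For numeric data, "Comparisons between 3 groups for normally distributed numeric variables will be done using the ANOVA", with Kruskal-Wallis as the non-normal alternative. For categorical data, "comparisons will be done by chi square test or fisher exact as appropriate". Then: "A p-value less than or equal to 0.05 will be considered statistically significant" and "All tests will be two tailed". One further sentence says that an equivalence limit will be checked between groups, without naming an outcome or a visit.

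The outcomes to which these tests apply are listed earlier. Under Clinical Performance Assessment: "Retention, marginal adaption, fracture of the restoration were scored using a modified United States Public Health Service (USPHS) criterion"; a plaque index and a gingival index; working time by stopwatch; and, at 12 months, parents' satisfaction with color, shape and size. Clinical and oral status are "assessed at follow-up periods of 3 (T1), 6 (T2), and 12 (T3) months". Under Microbiological analysis: "The number of Streptococcus Mutans, lactobacillus will be digitally counted", from swabs before preparation and at the same three follow-up times.

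The Sample Size calculation describes an equivalence trial that assumes no true difference. It uses 80% power, a two-sided 95% confidence interval and a margin of 0.6 in means, with 22 per group raised to 24 for losses. It does not say which outcome the 0.6 refers to.

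**The concern.** The threshold is unqualified, so it covers every outcome at every visit. Nothing in the plan ranks the outcomes, separates confirmatory from descriptive results, or limits which result may support a conclusion. One comparison with p at or below 0.05 could be reported as showing that a crown is better or worse, and the plan gives no means of telling it from a chance finding.

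This matters more here because the sample size rests on there being no difference between the crowns. If that assumption is right, any significant difference is false. The equivalence check does not protect against this, because it too is tied to no outcome or visit.

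**Working it through.** **The plan's own figure.** The document states no family-wise error rate. Its only sample-size result is 22 per group, which does not follow from its stated inputs because no standard deviation (SD) is given. With n = 2·SD²·(1.960 + 1.282)²/0.6²:

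- SD 0.5 gives 14.6, so 15 per group
- SD 0.6 gives 21.01, so 22 per group
- SD 0.7 gives 28.6, so 29 per group

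The 22 is therefore consistent with an assumed SD of about 0.6 on a single comparison of two means. It makes no provision for many outcomes.

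**Count of three-group tests.**

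| Outcome | All visits | 12 months only |
|---|---|---|
| Retention, marginal adaptation, fracture | 3 × 3 = 9 | 3 |
| Plaque and gingival indices | 2 × 3 = 6 | 2 |
| Two bacteria, after cementation | 2 × 3 = 6 | 2 |
| Satisfaction: color, shape, size | 3 | 3 (1 if summed) |
| Working time | 1 | 1 |
| **Total** | **25** | **11 (9 if summed)** |

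Baseline swabs would add 2, giving 27.

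**Chance of at least one false positive, independent tests of full size:** 1 − 0.95^m.

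- m = 25: 1 − 0.95²⁵ = 0.723
- m = 11: 1 − 0.95¹¹ = 0.431
- m = 9: 1 − 0.95⁹ = 0.370

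**Allowing for correlation and rare failures.** The document gives neither correlations nor failure rates, so these are assumed over a range. Null trials were simulated with all 25 tests and 24 per group, 4,000 runs per setting. The nine USPHS comparisons were either treated as full-size tests or analysed by exact Fisher tests with an assumed failure rate of 5% or 2%. The two correlations in the first column are within one outcome and between outcomes of the same domain.

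| Correlations | All tests full size | Fisher, 5% failures | Fisher, 2% failures |
|---|---|---|---|
| 0.3 / 0.1 | 0.71 | 0.59 | 0.54 |
| 0.5 / 0.3 | 0.67 | 0.56 | 0.51 |
| 0.7 / 0.5 | 0.59 | 0.50 | 0.46 |
| 0.8 / 0.5 | 0.56 | 0.46 | 0.43 |
| 0.9 / 0.7 | 0.46 | 0.41 | 0.36 |

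Across these settings and the independent case, the range is 0.36 to 0.72.

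**Below that range.** Suppose only 12 months is tested, satisfaction is summed, and failures are so rare that the three USPHS tests almost never reject. Six tests then remain: 1 − 0.95⁶ = 0.265 if independent. Correlation would lower this further. So 36% is the lowest simulated value, not a floor.

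**The case against.** **The count is inferred.** The plan does not say that each visit is tested separately or that color, shape and size are three tests. This stands, so 25 is an upper count for post-treatment three-group tests. Visit-by-visit testing is still the natural reading, because the plan names only one-time-point tests and no repeated-measures model. The 12-month-only reading does not remove the problem.

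**Stronger readings that the documents do not support:**

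- *A false positive is more likely than not.* This holds under independence and under low to moderate correlation. It fails with strong correlation, with exact tests on rare failures, or with 12-month-only testing. The documents do not settle which applies.
- *1.25 false positives are to be expected.* The product 25 × 0.05 = 1.25 needs every test to run at its full 5%. With exact tests at an actual size of about 0.012 (5% failures), it becomes 16 × 0.05 + 9 × 0.012 = 0.91.
- *Pairwise follow-ups raise the error to about 12% per outcome.* With three groups and no true difference, pairwise tests done only after a significant three-group test stay near 5% (simulated at about 5%). The 12% arises only if pairs are tested without that gate, which the plan does not describe.

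**The global null may not fit working time.** The groups undergo different procedures, so equal times are not a natural assumption. This stands, but it removes only one of the tests.

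**A blanket correction would be costly and would miss the design.** This also stands. The trial is sized for equivalence, so a remedy built only on adjusted difference tests would not say how equivalence is concluded. A wide confirmatory family would also lose much power.

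**Conclusion.** The concern holds as a matter of uncontrolled error, not as a claim that a false finding is probable. The plan applies one 0.05 threshold to up to 25 three-group tests and names nothing as primary. If no crown differs on any outcome, the chance of at least one false difference is roughly 36–72%. The upper end is for 25 independent full-size tests. The lower end depends on assumed strong correlation and rare failures with all 25 tests; independent testing at 12 months only gives 37–43%. Combining the favourable assumptions goes lower still, to about 26% or less, but remains well above 5% in the cases examined. The exact figure cannot be fixed from the document. These figures concern false claims of a difference; the error of falsely claiming equivalence is a separate matter.

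**What to change.** Replace the threshold sentence in Data Management and Analysis with text to this effect:

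> One primary outcome at 12 months (the outcome to which the 0.6 equivalence margin applies) is named before analysis. Confirmatory conclusions are limited to its two comparisons with zirconia (endocrown, Bioflex), each judged by whether the two-sided 95% CI lies within ±0.6. Any claim of a difference on this outcome uses Holm across the two comparisons. All other outcomes and visits are reported as estimates with 95% CIs, without significance claims.

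The sponsor must name that outcome. A 95% interval carries at most 0.025 error per equivalence claim, so the two claims together carry at most 2 × 0.025 = 0.05.

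**Cost.** No data collection changes. Nominal p-values at or below 0.05 on other outcomes can no longer be called significant. For a difference claim, power was computed by two-sided t-test with 22 per group and a true difference of 0.86 SD:

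- at 0.05: about 80%
- at 0.05/2 = 0.025 (first Holm step, two comparisons): about 70%
- at 0.05/8 = 0.00625 (a family of four domains by two comparisons): about 50%

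The last line is the reason to keep the confirmatory family at two.
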